6.3 Freedom from Major Amputation (Above the Ankle)

Freedom from major amputation of target limb (above the ankle) will be reported at 30 days, 6 months, and 12 months using data from 'Target Limb Amputation' CRF page.

Evaluable subjects: To be included in the denominator at a particular visit, the subject should have been followed-up beyond the beginning of the lower end of the respective visit window (23 days for 30 days, 150 days for 6 months, and 335 days for the 12 months) or the subject should have had a major amputation of target limb (above the ankle) event before the upper limit of visit window (37 days for 30 days, 210 days for 6 months, and 395 days for the 12 months).

The freedom from major amputation is based on the following definition:

Major amputation duration = (Date of Amputation - Date of Index Procedure).

Failure:Subject has a failure event if Major amputation of target limb is above the ankle
which includes Below knee or Through Knee or Above Knee.

Success: Subject has no failure event and is an evaluable subject as defined above.

Kaplan-Meier Analysis:

In addition to the analyses that are proportion-based, survival analysis will be performed (Kaplan-Meier estimate of survival function). Freedom from major amputation at 30 days, 6 months, and 12 months: the time to first event will be the time from index-procedure to the first occurrence of the first failure event, all subjects who have succeeded the major amputation endpoint will be censored at Day 395 if not discontinued (discontinued subjects will be censored at discontinuation day), and all the subjects with missing major amputation endpoint will be censored at the last available study day.

Binary outcome and Kaplan-Meier analyses for ATK, BTK and All UltraScore[™] subjects will be provided for the ITT population.

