6.2 Freedom from TLR

Target lesion information will be obtained from 'Core Lab Analysis – Angio Re-Intervention Analysis' CRF page. If for some reason the Angio data is missing, but there was TLR reported by site then Site Re-Intervention data will be used from 'Target Vessel Re-Intervention' CRF page. Freedom from TLR will be analyzed by subject at 30 days, 6 months, and 12 months visit.

Evaluable subjects: To be included in the denominator at a particular visit, the subject should have been followed-up beyond the beginning of the lower end of the respective visit window (23 days for 30 days, 150 days for 6 months, and 335 days for the 12 months) or the subject should have had a TLR event before the upper limit of visit window (37 days for 30 days, 210 days for 6 months, and 395 days for the 12 months).

The TLR (Re-intervention date) is based on the following definition:

TLR duration = (Date of TLR - Date of Index Procedure).

Failure: Subject has a failure event if Target Lesion Re-Intervention occurred before the upper limit of the respective visit window (Core Lab Angio CRF page). If TLR was reported by site but was missing in the Core lab page, then use Target Lesion Revascularization occurred before the upper limit of the visit window (Site Re-Intervention CRF page) as failure.

Success: Subject has no failure event and is an evaluable subject as defined above.

Kaplan-Meier Analysis:

In addition to the analyses that are proportion-based, survival analysis will be performed (Kaplan-Meier estimate of survival function). Freedom from TLR at 30 days, 6 months, and 12 months: the time to first event will be the time from index-procedure to the first occurrence

of the first failure event, all subjects who have succeeded the TLR endpoint will be censored at Day 395 if not discontinued (discontinued subjects will be censored at discontinuation day), and all the subjects with missing TLR endpoint will be censored at the last available study day.

Binary outcome and Kaplan-Meier analyses for ATK, BTK and All UltraScore[™] subjects will be provided for the ITT population.

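### SAP 6.3 leaves out the visit-window limit that SAP 6.2 states, so read as written a later amputation counts as a failure at earlier visits in the binary analysis

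*SAP*

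**What the plan says.** SAP 6.3 sets a per-visit endpoint: "Freedom from major amputation of target limb (above the ankle) will be reported at 30 days, 6 months, and 12 months". Its parts are as follows.

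- **Denominator.** There are two alternative routes. Either "the subject should have been followed-up beyond the beginning of the lower end of the respective visit window (23 days for 30 days", with 150 and 335 days for the later visits, or the subject had a major amputation "event before the upper limit of visit window (37 days for 30 days, 210 days for 6 months, and 395 days for the 12 months".
- **Event time.** "Major amputation duration = (Date of Amputation - Date of Index Procedure".
- **Failure.** "Subject has a failure event if Major amputation of target limb is above the ankle". The line then lists the levels that qualify (below, through or above the knee) and stops. It contains no day limit.
- **Success.** "Success: Subject has no failure event and is an evaluable subject as defined above".
- **Kaplan-Meier.** For the same endpoint, "the time to first event will be the time from index-procedure to the first occurrence of the first failure event".

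The corresponding failure line for TLR, in SAP 6.2, does carry a limit: "Subject has a failure event if Target Lesion Re-Intervention occurred before the upper limit of the respective visit window". SAP 6.2 repeats it for site-reported TLR, and SAP 6.5 applies it to the TLR component of patency.

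The definition in 6.3 is used again for the adjunctive-treatment subgroups (SAP 7.2) and for subjects treated with a drug-coated balloon (SAP 7.3.2).

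**The concern.** Sections 6.2 and 6.3 share almost the same structure, and the time limit is missing from one failure line only. Nothing else in 6.3 supplies it. Days 37, 210 and 395 appear only in the second route into the denominator. A subject followed past day 23 enters the 30-day denominator by the first route, whatever happens later. Once the subject is in, the failure line asks only whether the amputation was above the ankle. Because success requires no failure event, that subject cannot be a success at the early visit.

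Two things are at stake. First, the 30-day and 6-month proportions would absorb limb loss that happened after those visits, and the three reported rates would tend towards the same value. Second, the same table set would hold a binary proportion and a Kaplan-Meier estimate for the same endpoint and visit that differ because of the wording of one rule. The subgroups in SAP 7.2 and 7.3.2 inherit the problem with smaller denominators n, and each misplaced event moves a rate by 1/n.

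**Working it through.** The plan states no amputation rate and no sample-size figure tied to this endpoint, so there is no figure of its own to reproduce. The check has two parts.

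**1. One subject, both readings.** Take an amputation on day 304 (about month 10) and follow-up to day 365. The inputs from SAP 6.3 are lower limits of 23/150/335 days and upper limits of 37/210/395 days.

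| Visit | Evaluable by follow-up? | Failure line as written | With the 6.2 limit added |
|---|---|---|---|
| 30 days | 365 > 23, yes | failure | 304 > 37, success |
| 6 months | 365 > 150, yes | failure | 304 > 210, success |
| 12 months | 365 > 335, yes | failure | 304 < 395, failure |

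In the Kaplan-Meier analysis the event falls at day 304 under either reading, so the 30-day and 6-month estimates do not change.

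The 12-month proportion is the same under both readings if every amputation occurs before day 395. It differs only for a later one. SAP 6.6 provides for 12-month visits delayed past day 395, so such an event could be recorded.

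**2. Size in the binary proportions.** Let x37, x210 and x395 be the cumulative numbers of subjects with a major amputation by those days, and n the number evaluable. Assume that every subject is followed through the 12-month window and that no amputation falls after day 395.

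- Freedom with the limit, at visit v: 1 − x_v/n
- Freedom as written, at every visit: 1 − x395/n
- Understatement at visit v: (x395 − x_v)/n

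n = 175 is the approximate size of each cohort and n = 350 the maximum total (SAP 3.3). The event counts are assumptions chosen to span a range.

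| Assumed events by day 37/210/395 | n = 175, 30 days | n = 175, 6 months | n = 350, 30 days | n = 350, 6 months |
|---|---|---|---|---|
| 0/1/2 | 2/175 = 1.1 | 1/175 = 0.6 | 2/350 = 0.6 | 1/350 = 0.3 |
| 1/2/4 | 3/175 = 1.7 | 2/175 = 1.1 | 3/350 = 0.9 | 2/350 = 0.6 |
| 1/4/8 | 7/175 = 4.0 | 4/175 = 2.3 | 7/350 = 2.0 | 4/350 = 1.1 |
| 2/8/16 | 14/175 = 8.0 | 8/175 = 4.6 | 14/350 = 4.0 | 8/350 = 2.3 |

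Entries are percentage points. Two rows as rates at 30 days with n = 175, with exact (Clopper-Pearson) 95% intervals for illustration:

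- 1/2/4: 99.4% (96.9 to 100.0) with the limit, 97.7% (94.3 to 99.4) as written.
- 2/8/16: 98.9% (95.9 to 99.9) with the limit, 90.9% (85.6 to 94.7) as written.

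**The case against.** The strongest reply is that no one would program the endpoint this way. Section 6.3 reports at three visits, which means little if the rate barely changes between them. It ties amputations to days 37, 210 and 395 in the denominator rule, and it defines an amputation duration that has no use in the binary analysis unless events are dated against the windows. Its layout follows 6.2, where the limit is explicit, and the failure line may be there only to say which levels qualify. SAP 7.3.3 points the same way: freedom from death has no failure line at all and leaves timing to the windowed denominator and a duration. The Kaplan-Meier analysis is correct in any case and would expose a programming slip. The endpoint is secondary and descriptive, and the study has no formal hypothesis.

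Most of this stands. It makes a windowed intent likely and limits the damage to the binary proportions. It does not make the written rule right. Section 6.3, unlike 7.3.3, does have a failure line, and that line omits the limit. A programmer who follows it gets wrong early rates, and one who adds the window departs from the SAP without a record.

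A reader might also infer that the SAP deliberately carries late amputations back to earlier visits, or that early freedom from amputation will be understated in every analysis. The documents do not support either. No section states a carry-back rule, and the Kaplan-Meier estimates at 30 days and 6 months are the same under both readings.

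**Conclusion.** The point holds as an error in a written rule, most likely a drafting omission. Applied literally, the binary proportions at 30 days and 6 months count amputations that occurred after those visits, and the 12-month proportion counts any after day 395.

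Across the assumed range, at n = 175, freedom from major amputation would be too low by 1.1 to 8.0 points at 30 days and 0.6 to 4.6 points at 6 months. For the same counts among 350 subjects, these figures halve. They rest on assumed event counts and on complete follow-up through the 12-month window. The true size depends on how many amputations occur after each early window, which the documents do not say. No test or decision rule depends on these rates, so the consequence is a misreported descriptive secondary endpoint and its subgroups.

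**What to change.** Reword the failure line in SAP 6.3 so that a subject fails at a given visit only if a major amputation of the target limb (below-knee, through-knee or above-knee) is dated before that visit window's upper limit: day 37, 210 or 395. This matches SAP 6.2 and puts the amputation duration already defined in 6.3 to use. SAP 7.3.2 refers back to 6.3 and SAP 7.2 follows the methods of section 6, so both take up the change without further edits.

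The cost is one sentence in the SAP. It needs no new data, because the amputation date is already an input to the defined duration, and it changes nothing in the study design.

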6.4 Improved Clinical Measures from Baseline (ABI, Rutherford)

ABI:

Resting ABI measurements of the target limb will be summarized at 30 days, 6 months, and 12 months. Absolute values and change from baseline value will be summarized at each visit by subject. Absolute values and change from baseline values will be reported as continuous variable including N, mean, standard deviation, median, minimum and maximum.

Analyses for ATK, BTK and All UltraScore[™] subjects will be provided for the ITT population.

Rutherford:

Rutherford classification of the target limb will be summarized at 30 days, 6 months, and 12 months. Proportion of subjects on each category will be summarized at each visit by subject. A shift table from baseline will be presented with categories as improved, same and worsened.

Analyses for ATK, BTK and All UltraScore[™] subjects will be provided for the ITT population.

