6.1.3 Baseline Examinations

Each subject will have the following baseline examinations performed prior to the index procedure:

- The subject's demographic information (e.g., date of birth, sex, etc.)
- The subject's medical history, including antiplatelet/anticoagulation medications
- The subject's risk factors (e.g., diabetes, hypertension, dyslipidemia, etc.)
- Rutherford Classification
- Ankle Brachial Index (ABI) for treated limb only

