6.2 Index Procedure

This study is collecting data on an F.D.A. cleared medical device, consistent with the product IFU. Examinations, evaluations, procedural preparation, angiography, treatment, and hospital discharge procedures will be conducted per the investigational site's standard of care. Treatment with the UltraScoreTM Focused Force PTA balloon will be per the investigational site's standard of care and adhere to the IFU. For detailed information on device use and procedural and medication recommendations, reference the IFU. Data collected for this study include:

• Demographics and procedural information (e.g., target lesion type, TASC classification, location and length, degree of calcification, adjunctive treatment(s), baseline stenosis, etc.)

• Procedural outcomes (e.g., residual stenosis, flow limiting dissections, target lesion adjunctive treatments, etc.)

Investigators are able to treat one (1) target lesion as the study lesion, per patient in this study. The investigator may use his or her medical judgment as to which lesion becomes the study target lesion if a subject has multiple eligible lesions.

ATK subjects will be those that have a target lesion of the SFA or the popliteal artery. BTK subjects will be those that have a target lesion in the infra-popliteal arteries (posterior tibial, anterior tibial, and peroneal arteries). For this study, ATK arteries (SFA and popliteal) will end at the takeoff of the first tibial artery.

Lesions that cross from ATK to BTK may not be treated as the study target lesion.

Diffuse lesions will be considered separate lesions if there is 2 cm of healthy tissue between lesions.

Standard of care treatment of non-target lesions is allowed.

See the Instructions for Use for inflation and hold time recommendations.

Subjects are considered enrolled in the study when the UltraScore balloon is introduced into the subject.

If an angiographically acceptable result cannot be obtained after two inflations of the UltraScore[™] balloon (>30% residual stenosis), the subject should be considered a treatment failure. Subjects will continue to be seen at the protocol specified follow-up time points.

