7.5 Evaluation of Secondary Endpoints

The following secondary endpoints will be reported at the index procedure or through 12 months at these time points: 30 days, 6 months, and 12 months.

After UltraScore[™] Focused Force PTA balloon:

• Rate of bail-out stenting due to dissection

Through follow-up (30 days, 6 and 12 months):

- Freedom from TLR
- Freedom from major amputation (above the ankle)
- Improved clinical measures from baseline (ABI, Rutherford)
- Primary patency for ATK subjects only (as measured by DUS core lab; a PSVR ≥2.5 suggests 50% restenosis)

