3.3 Sample Size Consideration

There is no formal statistical hypothesis for this study. This study will enroll up to a maximum 350 subjects at approximately 45 sites. This will allow for approximately 175 subjects in an above the knee (ATK) cohort and 175 subjects in a below the knee (BTK) cohort. No site will be allowed to enroll more than 20% of the overall number of subjects to ensure the study be reasonably well balanced. The sample size is based on potential adequacy of data to meet the study objectives; it is not based on any statistical consideration.

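### SAP 6.4 sets no validity limit for ABI and no definition of ABI improvement, so falsely high readings enter the mean and SD of change as if real

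*SAP*

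**What the plan says.** Protocol section 7.5 lists the secondary endpoint as "Improved clinical measures from baseline (ABI, Rutherford", and SAP section 2.2.2 repeats it. Protocol section 6.1.3 asks at baseline for "Ankle Brachial Index (ABI) for treated limb only". Protocol Appendix B and SAP Table 1 schedule resting ABI at every follow-up visit.

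SAP section 6.4 sets out the analysis: "Resting ABI measurements of the target limb will be summarized at 30 days, 6 months, and 12 months". It then adds: "Absolute values and change from baseline values will be reported as continuous variable including N, mean, standard deviation, median, minimum and maximum". For Rutherford the same section goes further: "A shift table from baseline will be presented with categories as improved, same and worsened". No matching categories are given for ABI. On cohorts it says: "Analyses for ATK, BTK and All UltraScore[™] subjects will be provided for the ITT population".

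Neither document gives an upper limit for a valid ABI, a category for non-compressible arteries, an alternative measurement, or a sensitivity summary. Protocol section 7.3 bases rates on available data and does not impute missing data.

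**The concern.** ABI is informative only while the cuff can compress the ankle arteries. When they are too calcified to compress, the reading is high whatever the flow. That is general clinical knowledge; the documents do not discuss it. The population makes such readings foreseeable. Infra-popliteal lesions are eligible, only Rutherford category 6 is excluded, and diabetes and renal disease are recorded but are not exclusions.

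The SAP applies evaluability rules to other measured endpoints. Primary patency (SAP 6.5) and the COVID-19 restenosis analysis (SAP 6.6) require a valid stenosis category, and both primary endpoints have a not-evaluable class. ABI has no such rule. The gap matters somewhat more for BTK subjects, because they have no required duplex ultrasound and no patency endpoint. ABI is then the only scheduled haemodynamic measure in that cohort.

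Two things are at stake: whether the mean and SD of ABI change can be interpreted, and whether the handling of implausible values is fixed before anyone sees them. A lesser point is that an endpoint named as improvement has no stated way of judging improvement on ABI.

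**Working it through.** The plan has no figure to reproduce. It gives no ABI target, SD, test or confidence interval, and the sample size is declared non-statistical. The only input below taken from the documents is the cohort size, "approximately 175 subjects in an above the knee (ATK) cohort and 175 subjects in a below the knee (BTK) cohort". All other inputs are assumptions, used to show how the summary behaves.

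**1. False reading at one visit only.** Assume baseline 0.65 (SD 0.15), an independent true change of +0.15 (SD 0.15), so true follow-up averages 0.80, and a non-compressible reading of 1.5. Let p_F be the share falsely high at follow-up only and p_B the share falsely high at baseline only.

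- A false follow-up reading gives a mean change of 1.5 − 0.65 = +0.85. A false baseline reading gives 0.80 − 1.5 = −0.70.
- Mean = (1 − p_F − p_B)(0.15) + 0.85 p_F − 0.70 p_B = 0.15 + 0.70 p_F − 0.85 p_B.
- Mean square = (1 − p_F − p_B)(0.15² + 0.15²) + p_F(0.85² + 0.15²) + p_B(0.70² + 0.15² + 0.15²) = 0.045(1 − p_F − p_B) + 0.745 p_F + 0.535 p_B. SD = √(mean square − mean²).

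| p_F | p_B | Mean | SD | Median (simulated) |
|---|---|---|---|---|
| 0 | 0 | 0.150 | 0.150 | 0.150 |
| 5% | 5% | 0.150 + 0.035 − 0.0425 = 0.143 | √(0.1045 − 0.0203) = 0.290 | 0.150 |
| 8% | 3% | 0.150 + 0.056 − 0.0255 = 0.181 | √(0.1157 − 0.0326) = 0.288 | 0.161 |
| 3% | 8% | 0.150 + 0.021 − 0.068 = 0.103 | √(0.1052 − 0.0106) = 0.308 | 0.140 |

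The mean moves by about −30% to +20% only when the two shares are unequal. With equal shares it falls by 5%. The SD roughly doubles in all three artefact cases.

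**2. False reading at both visits.** With the same inputs, let 8% read 1.5 at baseline and at follow-up, so that their change is 0.

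- Mean = 0.92 × 0.15 = 0.138.
- SD = √(0.92 × 0.045 − 0.138²) = √(0.0414 − 0.0190) = 0.150.

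The mean falls by 8% and the SD does not rise. This is dilution towards zero.

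**3. Second set of assumptions, n = 175.** True change 0.15, SD 0.20, and a false reading that adds 0.4 to 0.8 at one visit. The yardstick is the 95% half-width of a mean, 1.96 × 0.20/√175 = 0.030; the SAP itself plans no such interval.

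- Follow-up only, 5%: shift 0.05 × 0.4 = 0.02 to 0.05 × 0.8 = 0.04; mean 0.17 to 0.19.
- Follow-up only, 10%: shift 0.04 to 0.08; mean 0.19 to 0.23, median about 0.18.
- Baseline only, 10%: mean 0.07 to 0.11, median about 0.12.
- Equal shares of 5% or 10% each way: mean and median stay at 0.15; SD 0.24 to 0.41.
- Both visits with change masked to 0: mean 0.90 × 0.15 = 0.135 at 10%, and 0.70 × 0.15 = 0.105 at 30%.

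A one-directional artefact in 10% of a cohort moves the mean by more than 0.030. The median moves less, but it is not immune.

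**4. In numbers of subjects.** On the inputs of step 1, five of 175 subjects reading 1.5 in place of 0.80 at follow-up move the cohort mean by 5 × 0.70/175 = 0.02.

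**The case against.** The strongest reply is that the planned table already protects the reader. Section 6.4 lists the median, minimum and maximum beside the mean. An extreme reading would show in the range, and the median resists it. ABI is one half of one secondary endpoint, with no hypothesis, test, interval or success criterion. ATK and BTK are shown separately, and the Rutherford half is untouched. All of this stands, and it keeps the point minor. What it leaves open is what happens to an implausible value once seen, and which summary is then reported.

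A second reply is that sites may already leave such readings blank. That is possible, since the ABI case report form and site instructions are not in the documents. If so, the readings drop out uncounted, and practice may differ between sites.

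Several stronger readings are tempting, and the documents do not support them:

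- *That the plan treats a higher ABI as always better, or counts false readings as improvements or losses.* No passage does so. No improvement rule for ABI exists at all.
- *That the mean is the main ABI result.* No statistic is singled out.
- *That the distortion falls mainly in BTK, or that ATK–BTK differences would reflect calcification.* The documents give no frequency for either cohort. The calcification in Protocol 6.2 ("target lesion type, TASC classification, location and length, degree of calcification, adjunctive treatment(s), baseline stenosis, etc") is listed among target-lesion characteristics; it is not a record of the ankle arteries under the cuff.
- *That the SD will double or the mean move by a given percentage.* This requires the artefact at one visit only. If calcification persists across visits, step 2 of the working applies instead.

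**Conclusion.** The point holds as a minor gap. Followed as written, SAP 6.4 admits every recorded resting ABI into the absolute and change summaries, so a falsely high reading is treated as real. The size and direction of the effect are unknown. On the assumptions of steps 1 and 2, the mean change could lie anywhere from about 0.10 to 0.18 against a true 0.15, with an SD between 0.15 and 0.31, depending on how many readings are affected, at which visit, and whether the artefact persists. Those figures rest on assumed ABI levels, shares and artefact size; none comes from the documents. The missing definition of ABI improvement needs no assumption: it is plain from comparing the ABI and Rutherford paragraphs of section 6.4. No primary endpoint or formal conclusion of the study is affected.

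**What to change.** Amend SAP section 6.4 before database lock:

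- Treat an ABI reading above a pre-set validity limit as not evaluable at that visit, with the value confirmed by the lead investigators. Do the same for a reading flagged as non-compressible, if the case report form captures this.
- Report the number of such readings by cohort and visit.
- Present the change summary in subjects with valid readings at both baseline and the visit, with the already planned median shown alongside the mean.
- Keep the all-readings summary as a sensitivity row, so that the exclusions cannot look selective.
- Report the proportions improved, same and worsened on ABI among valid pairs, using a margin stated in advance. Without a margin, about half of subjects would appear improved under zero true change and symmetric measurement error.

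The cost is SAP wording, a few table rows and a somewhat smaller N for ABI. A rule based on the recorded value needs no new data. A rule based on a non-compressible flag works only if that field exists, which the documents do not show.
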